
mini-vaccination stations in communities highly impacted by the pandemic and identifying individual and structural barriers to COVID-19 immunization (Phase 2). Specific aims include:

Aim 1. To evaluate the preliminary impact of 2VIDA! compared to the standard-of-care for COVID-19 vaccination services among Latinx and AA adults ≥ 16 years (N=1000) in San Diego. We will use a 2-armed randomized controlled trial (RCT)* where Latinx and AA adults ≥ 16 years or older from six participating community health centers (CHC) and surrounding communities will be assigned to the 2VIDA! intervention (n=3 CHC; N=500 participants) or to the control site (e.g., standard of care) (n=3 CHC; N=500 participants). Data will be collected on a) sociodemographic characteristics; b) characteristics associated with social marginalization; c) access to and utilization of health care; d) vaccination history, interest, hesitancy and uptake; e) perceptions of the COVID-19 vaccine (e.g., fears, myths, etc.); f) general health; and h) trust in government, research, and social agencies, i) satisfaction with 2VIDA!; at baseline and 4-week follow-up. We hypothesize that at follow-up, compared to control participants, 2VIDA! participants will:

H.1. have increased knowledge about the COVID-19 vaccine (including medically accurate information, benefits, and risks);
H.2. more likely to receive the COVID-19 vaccine;
H.3. more likely to complete vaccine series (based on Centers for Disease Control and Prevention [CDC] recommendations).¹

Aim 2. To assess feasibility, acceptability, and intervention effects of 2VIDA! To assess feasibility and acceptability, we will utilize quantitative methods to track recruitment, condition assignment, participant retention, intervention implementation, and potential threats (e.g., contamination). We will also utilize qualitative methods to assess acceptability via focus groups with participants to understand potential for broad implementation (e.g., what components did they receive of the intervention, client satisfaction, linkage to COVID-19 services). To assess intervention effects, we will examine participant vaccination rates/completion across both groups.

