PHASE II. To evaluate the preliminary impact of 2VIDA! compared to the standard-of-care for COVID-19 vaccination services among Latinx and AA adults >16 years (N=1000) in San Diego. During Phase 2 we will offer the COVID-19 vaccine at the participating SYH community health centers and mini-vaccination stations that will be set-up in these communities (only intervention sites) as part of the intervention efforts (i.e., research activities) to increase access and uptake of the COVID-19 vaccine. We have identified various open spaces (e.g., public parks) in these communities to set-up the vaccination stations. SYH is currently offering the vaccine in their facilities as part of their standard of care. It is available to everyone who is eligible according to the state guidelines and does not depend on participating in this study. However, as part of 2VIDA! we will add these mini-vaccination stations to increase access to the vaccine (e.g., open after 5:00pm and on the weekends). Furthermore, data will be collected to assess individual, social, and contextual factors related to access, acceptance, and uptake of the COVID-19 vaccine including: a) sociodemographic characteristics; b) characteristics associated with social marginalization (e.g., homelessness, food insecurity); c) access to and utilization of health care; d) vaccination history, interest, hesitancy and uptake; e) perceptions of the COVID-19 vaccine (e.g., fears, myths, etc.); f) general health; and h) trust in government, research, and social agencies; i) satisfaction with 2VIDA! at baseline and 4-week follow-up. The survey will last approximately 20 minutes and will be self-administered in both English and Spanish. Following the survey participants will be offered the COVID-19 vaccine and the SYH staff will help them set-up an online appointment onsite for the 2nd dose (1 month follow-up) and will be asked to complete a 5 min survey during the follow-up visit. SYH has trained medical staff and a strict protocol for the storage, handling, and application of the vaccine. UCSD staff will not be involved in this process. Furthermore, participants will be asked to provide separate written consent in order to receive the vaccine that will be conducted by SYH staff. Additionally, two focus groups (FGs) will be conducted with members of Latinx and AA communities (n=8-10 participants per group) to obtain feedback on implementation and ways to improve future sustainability and scalability for future vaccination efforts among vulnerable underserved communities. FGs will be transcribed and reviewed for themes specific to 2VIDA! including personal and structural barriers to medical accurate information and the COVID-19 vaccine, benefits, challenges, feasibility, and scalability.

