Cover Page for ClinicalTrials.gov

Document: Statistical Analysis Plan

Official Study Title: Project 2VIDA! COVID-19 Vaccine Intervention Delivery for Adults in Southern California

NCT number: NCT05022472

Document date: February 5, 2021

STATISTICAL DESIGN AND POWER CALCULATIONS

We will approach overall data analyses using a multivariate repeated measures design (i.e., doubly multivariate) to assess mean differences in treatment and control groups on our primary (acceptance of COVID-19 vaccine and vaccine series completion) and secondary outcome variables (increased knowledge of COVID-19 vaccine, increased access to COVID-19 vaccine, vaccine hesitancy). Additional measures at baseline and follow-up will be used as covariates (e.g., outreach and health communication, vaccine hesitancy or mistrust). Mean differences, both within and between treatment and control groups as well as group by treatment interaction effects will be analyzed. The targeted sample size is sufficient to detect a small effect size (.20) with power = .90 at alpha = .05 accounting for moderate participant attrition. Descriptive Statistics. To describe the overall sample regarding demographics, structural and individual barriers, and potential covariates of intervention effects at baseline, prevalence statistics and means and standard deviation will be provided for all baseline variables; Cronbach's alpha of .70 will be required to be considered reliable. Baseline Analyses to Detect Differences Between Treatment Groups. Chi-square analyses and paired t-tests will be used to detect differences in demographics, knowledge of COVID-19 vaccine, access to COVID-19 vaccine, acceptance of COVID-19 vaccine and series completion, COVID-19 resource-seeking behaviors and linkage into care between intervention and control groups. Demographic variables included in these analyses will be age, gender, race/ethnicity, household income, marital status, and having insurance. Those variables differing across treatment groups at the $p < .20$ level will be included in subsequent adjusted outcome analyses.

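### The SAP plans within-arm tests beside the between-arm contrast without saying which decides effectiveness; for vaccine receipt and series completion, a within-arm rise is no evidence about 2VIDA!

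*SAP*

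**What the plan says.** The SAP describes one doubly multivariate repeated-measures analysis. It says that "Mean differences, both within and between treatment and control groups" will be examined, and that "group by treatment interaction effects will be analyzed". Protocol section 8 (Data Analysis) repeats this. Neither document ranks these results or says which one supports a claim that 2VIDA! works.

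The outcomes are "primary (acceptance of COVID-19 vaccine and vaccine series completion") and "secondary outcome variables (increased knowledge of COVID-19 vaccine, increased access to COVID-19 vaccine, vaccine hesitancy"). Acceptance is not defined as receipt or as willingness. The SAP's baseline analyses list acceptance and series completion among the variables measured at baseline, so a change from baseline can be tested.

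The hypotheses are worded differently from the analysis. Protocol section 5 (Aim 1) opens them with "We hypothesize that at follow-up, compared to control participants, 2VIDA! participants will" and then lists knowledge (H.1), vaccine receipt (H.2) and series completion (H.3).

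On timing, Protocol section 8 (Phase II) states: "Following the survey participants will be offered the COVID-19 vaccine". It adds that SYH already offers the vaccine at its facilities as standard of care.

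**The concern.** Receipt of a vaccine and completion of a series are cumulative. A participant can move from no to yes between baseline and four weeks but cannot move back. With the vaccine on offer in both arms after baseline, some rise is expected in each arm with or without 2VIDA!. A within-arm test on these outcomes asks whether anyone was vaccinated, which is not what H.2 and H.3 ask.

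Two misreadings are then open. One is to cite a significant rise in the 2VIDA! arm as an effect of 2VIDA!. The other is to cite significance in one arm and not in the other as a difference between arms. The plan's wording guards against neither.

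The interaction term adds to this. Group and treatment are the same factor here, so the term as written does not clearly compare change between arms. Group by time is presumably meant.

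**Working it through.** **Inputs from the documents.** 500 participants and 3 clinics per arm, randomised by clinic (Protocol sections 5 and 10); surveys at baseline and four weeks (section 5); alpha .05 (SAP).

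**Assumptions.** Two-sided tests. 400 analysed per arm, which is 500 × (1 − 0.20); the SAP calls attrition moderate and gives no rate. Four-week uptake, meaning the share of analysed participants who change from no to yes, is not given, so a range is used.

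**1. The plan's own figure.** The SAP calls the sample "sufficient to detect a small effect size (.20") with "power = .90 at alpha = .05 accounting for moderate participant attrition". Read as a standardised difference d = 0.20 in a two-sided comparison of two means, n per arm = 2 × (1.960 + 1.282)² / 0.20² ≈ 526. Power = Φ(0.20 × √(n/2) − 1.96) gives 0.885 at n = 500 and 0.807 at n = 400. Other readings reach about .90: one-sided with 15% attrition (0.898), or baseline adjustment with an assumed correlation of .5 and 20% attrition (0.904). The test, sidedness and attrition rate are not given, so the figure can be neither confirmed nor called wrong. The within-arm point does not depend on it.

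**2. Changes needed for within-arm significance.** When all k changes go one way, exact McNemar p = 2 × (1/2)^k.
- k = 5: p = .0625
- k = 6: p = .031
- k = 8: p = .008

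Six new vaccinations are enough: 6/500 = 1.2%, or 6/400 = 1.5%. A paired t-test on the 0/1 change, closer to the SAP's mean differences, needs only four (p = .045).

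**3. How often this happens with no 2VIDA! effect.** Let K be binomial (400, uptake) in each arm, with the same uptake in both, and let P = Pr(K ≥ 6). Both arms are significant with probability P², exactly one with 2P(1 − P).

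| Four-week uptake | P, one arm | Both arms | Exactly one arm |
|---|---|---|---|
| 1% | 0.214 | 0.046 | 0.337 |
| 2% | 0.812 | 0.659 | 0.306 |
| 3% | 0.981 | 0.962 | 0.037 |
| 5% | >0.999 | >0.999 | <0.001 |

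At 1% and 2% uptake the both-arms figure is 0.148 and 0.874 with 500 analysed per arm, and 0.020 and 0.493 with 350.

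**4. The between-arm test on the same data.** In 20,000 simulated trials per scenario, with equal uptake from 2% to 60% and 400 per arm, the between-arm test rejected in 4% to 5%, as it should. With 20% uptake under 2VIDA! and 30% under control, a harmful effect, both within-arm tests were still significant in essentially every trial. These simulations include no variation between clinics.

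**5. If clinics were respected within an arm.** A test on 3 clinic-level changes (2 degrees of freedom, 133 analysed per clinic) at 10% uptake is significant with probability about 0.63 at an assumed intraclass correlation (ICC) of .01, and 0.25 at .05. Significance is then far from automatic.

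**6. Outcomes that move both ways.** With no net change and 5%, 10% or 20% of participants moving in each direction, the exact within-arm test rejected in about 2% to 4%. The one-way argument does not carry over to these outcomes.

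**The case against.** The strongest reply is that no passage makes a within-arm p-value the criterion for effectiveness. A repeated-measures model yields within, between and interaction terms as a matter of course, and listing them may only describe the model. The SAP also plans the between-arm contrast, and every hypothesis is against control. This stands. A reader might infer that the trial has the wrong primary test, or will report a within-arm rise as efficacy. The documents do not say so. What remains is an invalid route to a conclusion left open beside a valid one.

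A second reply is that significance in both arms is not assured. This stands too. A reader might infer that both within-arm tests must be significant whatever 2VIDA! does, or that their false-positive rate is near 100%. Either claim needs an uptake figure the documents lack, and Protocol section 5 reports low uptake at SYH. That remark describes SYH generally, whereas trial participants are offered the vaccine straight after the survey, so higher uptake is plausible but not established. Nor is rejection strictly a false positive: if people were vaccinated, the null of no change is false. The error lies in crediting the change to 2VIDA!. Low uptake does not rescue the within-arm tests, because that is where one arm alone is often significant by chance.

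A third reply is that the calculation treats participants as independent. The SAP mentions no clustering, so this matches its apparent approach, but it is an assumption.

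**Conclusion.** The point holds as a gap in the inferential plan. The SAP sets no order between within-arm and between-arm results, and for vaccine receipt and series completion the within-arm result carries no information about 2VIDA!. With individual-level exact tests, 400 analysed per arm and equal uptake, both arms are significant in about 5% of trials at 1% uptake, rising to over 99.9% at 5% or more. The uptake range, the 20% attrition and the independence of participants are all assumptions.

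The one-way argument is limited to receipt and completion. It should not be extended to knowledge, access or hesitancy, nor to acceptance if that means willingness. For those outcomes the weaker point applies: within-arm change is uncontrolled and also reflects the general roll-out, outside incentives (noted in Protocol section 11) and being asked twice.

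**What to change.** In the SAP and in Protocol section 8 (Data Analysis):

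- State that conclusions about effectiveness rest only on the between-arm contrast, either the difference at follow-up or the group-by-time term, and correct the interaction wording accordingly.
- For receipt and series completion, report a between-arm risk difference with an interval that respects the randomised clinics, for example from clinic-level proportions with 3 + 3 − 2 = 4 degrees of freedom.
- Report within-arm change descriptively, without p-values.
- State whether acceptance means receipt or willingness.

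No new data are needed. The cost is a wording change, modest analysis work, and wider, less favourable intervals. As an illustration, with 500/3 ≈ 167 per clinic the design effect is 1 + 165.7 × ICC. That is 2.66 at an assumed ICC of .01 and 9.28 at .05, so intervals widen by about √2.66 ≈ 1.6 and √9.28 ≈ 3.0 times, before any allowance for having so few clinics. That width follows from randomising six clinics; the change only makes it visible.

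### One omnibus comparison of repeated-measures means gives the yes/no hypotheses H.2 and H.3 no test or effect measure of their own, names an interaction that cannot be estimated on its natural reading, and leaves out clinic

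*SAP*

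**What the plan says.** The SAP (Statistical Design and Power Calculations), repeated in protocol section 8 under Data Analysis, sets out a single approach for all outcomes: a "multivariate repeated measures design (i.e., doubly multivariate) to assess mean differences in treatment and control groups". The outcomes in it are "primary (acceptance of COVID-19 vaccine and vaccine series completion" as primaries, with knowledge, access and hesitancy as secondaries. The contrasts are given in one sentence: "Mean differences, both within and between treatment and control groups as well as group by treatment interaction effects will be analyzed".

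Protocol section 5 describes a "2-armed randomized controlled trial (RCT" design with data collected "at baseline and 4-week follow-up". Its hypotheses are that 2VIDA! participants will be "more likely to receive the COVID-19 vaccine" (H.2) and "more likely to complete vaccine series" (H.3). Section 8, Phase II, places the offer of vaccine after the baseline survey. Section 10 says that six clinics are randomized evenly to the two conditions.

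No risk difference, odds ratio or other measure for a proportion is named for follow-up. Chi-square tests appear only among the baseline comparisons. Aim 2 says vaccination and completion rates will be examined in both groups, without naming a test. Neither document defines acceptance or says whether it is the same thing as receipt in H.2.

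**The concern.** Four things do not fit together.

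- **Omnibus test.** A doubly multivariate test asks whether any outcome, at any time, differs. A significant result does not say that receipt or completion differs, and those are the events H.2 and H.3 are about.
- **Baseline.** Study doses come after the baseline survey, so receipt and completion carry little or no baseline information. A repeated-measures change adds little to a plain comparison at 4 weeks.
- **Interaction.** The SAP calls the arms treatment and control groups, then says "group by treatment interaction effects will be analyzed". On that usage the term is arm by arm. The contrast that would compare change between arms is arm by time, and it is not mentioned.
- **Clinic.** Clinics are the unit of randomization, but the model treats participants as independent.

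At stake is whether the trial can report a clear answer on its two primary questions with an error rate near the stated .05.

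**Working it through.** **Inputs from the documents.** 500 participants per arm; six clinics, three per arm (protocol sections 5 and 10); two measurement times; effect size .20, alpha .05, power .90 (SAP). **Assumed, because the documents are silent:** two-sided test; .20 is a standardised mean difference d; baseline–follow-up correlation rho of .3, .5 or .7; intraclass correlation (ICC) of .01 or .05.

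**1. The plan's own figure.** Two-sided, d = .20 with 500 per arm: d × √(n/2) = .20 × √250 = 3.162, and power = Φ(3.162 − 1.96) = .885. That is close to .90, but with no attrition. At 10% attrition power is .851 and at 20% it is .807. The attrition wording is met under some variants, such as a one-sided test (.912 at 10%) or baseline adjustment with rho = .5 (.904 at 20%). The SAP does not say which was meant.

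**2. Can the interaction be estimated?** Code group and treatment both as arm. The columns intercept, group, treatment and group × treatment have rank 2 of 4, so neither a separate treatment effect nor the interaction can be estimated. Intercept, arm, time and arm × time have rank 4 of 4. So do intercept, arm, ethnicity and arm × ethnicity.

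**3. Scales: what if the time-averaged arm effect is used?** With no baseline difference and d = .20 at follow-up:
- time-averaged effect: standardised size (.20/2)/√((1 + rho)/2)
- arm by time: standardised size .20/√(2(1 − rho))
- power = Φ(size × √250 − 1.96)

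| rho | averaged size | power | arm-by-time size | power |
|---|---|---|---|---|
| .3 | .124 | .50 | .169 | .76 |
| .5 | .115 | .45 | .200 | .885 |
| .7 | .108 | .40 | .258 | .98 |

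These assume independent participants, so they show only the loss from choosing the wrong contrast.

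**4. What the omnibus test can hide.** Take five uncorrelated outcomes, 500 independent participants per arm, an assumed d = .30 on knowledge alone and no effect on receipt or completion. The noncentrality is 250 × .30² = 22.5 on 5 degrees of freedom, so the test is significant about 97% of the time. That result would say nothing about H.2 or H.3.

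**5. Yes/no data in a mean-difference test.** Simulated under no effect (20,000 runs per setting; rates of 3%, 14%, 50% and 80%; clinics of 166 or 167):

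| ICC | mean-difference test | clinic-level t-test, 4 df |
|---|---|---|
| 0 | .049–.053 | .046–.051 |
| .01 | .23–.24 | .045–.052 |
| .05 | .50–.52 | .035–.050 |

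The design effect gives the same picture. At ICC .01 it is 1 + (1000/6 − 1) × .01 = 2.66, and 2Φ(−1.96/√2.66) = .23. At ICC .05 it is 9.28, which gives .52. Without clustering, chi-square has the same error rate as the mean-difference test. The yes/no scale is therefore not what breaks the test; omitting clinic is.

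**6. Does a binary test change the sample size?** At Cohen's h = .20 and control rates of 3% to 90%, ignoring clinics, 90% power needs 526 to 548 per arm, against 526 for the comparison of means. The figure barely moves.

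**The case against.** A reader might go further and infer that H.2 and H.3 have no valid stated test. The documents do not support that on the yes/no scale alone. The SAP does state a between-arm mean difference, and on 0/1 data that is a difference in proportions with about 5% type I error when participants are independent.

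A reader might also say that the interaction cannot exist. It fails only if group means arm. That is the natural reading, but the phrase could be a slip for group by time, or could mean ethnic group by treatment, and both can be estimated. A repeated-measures program would ordinarily fit arm by time even though the text omits it.

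It is tempting to say that averaging over a zero baseline halves the estimate. Against a constant zero, the difference and its standard error both halve, so the p-value does not change. Nor does the SAP say a time-average would be reported as the risk difference. Baseline may not be exactly zero either: the eligibility lists in protocol sections 8 and 12 do not exclude earlier vaccination. Acceptance could be an attitude scale.

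Finally, a reader might infer that participants without follow-up will be dropped and that measured completion will drift toward 100%. Complete-case analysis is the usual default for this model, but the SAP is silent on missing data and nothing in the documents sets the size of any drift. Follow-up by text or email for one-shot recipients, telephone or video options, and contact tracing of missed second doses all work against such loss.

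These points narrow the claim. They do not supply a test or effect measure for H.2 and H.3, define the interaction, or put clinic in the model.

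**Conclusion.** The point holds as a specification fault to be corrected before analysis. H.2 and H.3 have no separately specified test or effect measure. The interaction is not estimable on its natural reading, and the contrast the design needs is unnamed.

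For the scales, falling back on the time-averaged arm effect would cost between .26 and .58 of power over rho .3 to .7 (.76 − .50 and .98 − .40). That assumes d = .20, 500 per arm, independence and no attrition.

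The largest numerical consequence is the missing clinic term: type I error of about .23 at ICC .01 and about .50 at ICC .05. Both ICCs are assumptions, since the documents give none.

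**What to change.** 1. Define receipt and series completion as two separate binary outcomes at 4 weeks. Say how each relates to acceptance.
2. For each, report the risk difference between arms with a confidence interval, from clinic-level proportions or from a mixed model with a small-sample correction.
3. For the scales, replace group by treatment with arm by time in a mixed model that has a clinic term and uses all available data. Name the arm difference at follow-up as the reported contrast.
4. Analyse every enrolled participant in the arm of their clinic and state how those without follow-up are handled. This matters because two-shot participants complete the follow-up survey at the dose-2 visit (protocol section 8, Mini-vaccination stations), so missing surveys may be linked to missed completion.
5. Use SYH vaccine records for status only if linkage is permitted. Sections 14 and 15 say that the survey code does not link to identity, restrict the contact list to scheduling, delete identifiers after follow-up and send no identifiers to UCSD. Record linkage might therefore need a protocol, consent and IRB change.

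Items 1 to 4 cost SAP wording and standard software, with no new participants or visits. The real price is precision. With six clinics the comparison rests on about 4 degrees of freedom, so intervals will be wider than the stated power suggests. At ICC .01, 500 per arm carries the information of about 188 independent participants (500/2.66).

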10. RECRUITMENT

Six SYHealth community health centers across San Diego County have been selected based on their serving predominantly Latinx and AA client population and having the Zip codes with the highest number of COVID-19 cases in the County. These clinics are located in National City, Logan Heights, Lincoln Park, Valencia Park and San Ysidro. Each clinic will be randomly selected and randomized evenly to either the intervention or control conditions, using computer-generated randomization plans prepared using SAS statistical software under the direction of the lead study statistician. Clinic-level randomization was selected to minimize between-arm contamination of intervention and control conditions. Participants from both intervention (n=500) and control sites (n=500) will be recruited using reactive recruitment, including the use of community partner social media platforms, and flyers distributed in the SYH target health centers and high traffic, readily visible areas, where eligible participants are likely to see them (e.g., grocery stores, local CBO's, parks, barber shop, cafés, food banks, gyms, local restaurants). Flyers will include study information and contact information for study staff. Likewise, the project staff publicized the rapid vaccine effort (e.g., mini-vaccination stations) by posting flyers that noted locations, dates, and times of vaccine distribution, and through presentations about the project at community meetings. Project staffing, training, and support, including the selection of nurses and outreach staff (e.g., peer-health educators and research assistants) with complementary research skills and personal knowledge of the community will be key to the success of the project. Two bilingual Latinx (one male and one female) and two AA (one male and one female) outreach workers trained in research ethics and protocols, and familiar with this population will approach individuals who appear to be eligible (Latinx and AA adults ages 16 years or older) at the SYH community centers and mini-vaccination stations in the participating communities, confirm eligibility, and describe the study to those eligible. Research staff will update time logs and continuously update our sampling frame until recruitment is finalized. The reason for refusal or ineligibility will be recorded. Extensive efforts will be made to have an equal representation of Latinx and Black community members and at least 40% women.

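### The stated .90 power with attrition already allowed for is not supported: on the conventional reading 500 recruited per arm gives .885 with no loss and less with any

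*SAP*

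**What the plan says.** The only power statement in the SAP, under Statistical Design and Power Calculations, is that "The targeted sample size is sufficient to detect a small effect size (.20) with power = .90 at alpha = .05 accounting for moderate participant attrition". The Data Analysis paragraph in Protocol Section 8 carries the same sentence.

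The sample size is in the protocol. Aim 1 in Section 5 says participants "will be assigned to the 2VIDA! intervention (n=3 CHC; N=500 participants) or to the control site (e.g., standard of care) (n=3 CHC; N=500 participants"). Section 10 makes clear that these are recruitment numbers: "Participants from both intervention (n=500) and control sites (n=500) will be recruited using reactive recruitment". Losses to follow-up therefore come out of the 500.

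The planned analysis is a doubly multivariate repeated-measures model of mean differences, with two primary outcomes (vaccine acceptance and series completion) and further measures as covariates. Six clinics are randomised, three per arm.

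Neither document says what scale the .20 is on, whether alpha is one- or two-sided, what rate of attrition counts as moderate, what correlations were assumed, or which test the .90 refers to.

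**The concern.** The sentence makes two claims: .90 power for an effect of .20, and that this power remains after attrition. The second requires recruitment to exceed the number needed for analysis. On the usual reading of a small effect of .20, recruitment is below that number, so there is no allowance for loss.

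If the claim is unsupported, a null result will be read as more informative than it is. At an assumed 10% to 20% loss, the type II error on this reading is about 15% to 19%, against the stated 10%, before any effect of clinic randomisation.

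**Working it through.** **Inputs from the documents.** Effect .20, power .90, alpha .05 (SAP); 500 recruited per arm, 1:1 (Protocol Sections 5 and 10).

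**Assumptions, because the documents are silent.** The effect is a standardised mean difference d; the test is two-sided, unadjusted and two-sample; participants are independent; attrition runs from 0% to 25%.

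**1. Number needed for the stated .90.** By normal approximation, n per arm = 2(z₀.₉₇₅ + z₀.₉₀)²/d² = 2(1.960 + 1.282)²/0.04 = 525.4, so 526. The exact noncentral t calculation gives 527. The plan recruits 500.

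**2. Power at the numbers left after attrition.** Noncentral t with noncentrality d√(n/2). At n = 500 this is 0.20 × √250 = 3.162, which gives .885.

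| Attrition (assumed) | Analysed per arm | Power for d = .20 |
|---|---|---|
| 0% | 500 | .885 |
| 5% | 475 | .869 |
| 10% | 450 | .850 |
| 15% | 425 | .830 |
| 20% | 400 | .807 |
| 25% | 375 | .781 |

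The .90 is approximated (within 1.5 points) only with no attrition. Reading .20 as Cohen's h on a proportion gives nearly the same figures: .882 to .886 at 0% and .777 to .782 at 25%, for control rates from 10% to 70%.

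**3. Difference detectable with .90 power.** d = .205, .216 and .229 at 0%, 10% and 20% attrition.

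**4. Other readings that could give about .90 after attrition.**

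- *One-sided .05.* Needs 429 per arm. Power is .912 at 10% loss, .898 at 15% and .881 at 20%.
- *Adjustment for baseline or other covariates, two-sided.* The number needed becomes 525.4(1 − R²). Setting this to 450 gives R² = 1 − 450/525.4 = .14 (correlation about .38). Setting it to 400 gives R² = 1 − 400/525.4 = .24 (correlation about .49).
- *Joint test of the two primary outcomes (Hotelling T²), d = .20 on both.* Noncentrality is (n/2) × .08/(1 + ρ), where ρ is the correlation between outcomes. With ρ = .3, power is .924 at 10% loss and .890 at 20%. With ρ = .5 it is .882 and .840; with ρ = .7, .837 and .788.
- *Effect read as Cohen's f = .20.* Power exceeds .99, but f = .20 corresponds to d = .40, which does not fit the description of a small effect.

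**5. Clinics.** None of these readings allows for clinic randomisation. Assume an intraclass correlation of .001 and 20% attrition. Clinic size is 400/3 = 133.3, the design effect is 1 + 132.3 × .001 = 1.13, and the effective number is 400/1.13, about 353 per arm. Power for the unadjusted two-sided comparison is then about .76 by normal approximation, or .52 with the 4 degrees of freedom that six clinics leave. At an assumed .01 these become .46 and .30.

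**The case against.** The strongest reply is that the documents leave so much unstated that the sentence cannot be shown to be false. That stands. A reader might infer that the claim is refuted by its own arithmetic. It is not, because sidedness, metric, attrition rate and correlation all had to be supplied here. The gap at zero attrition, .885 against .90, is small enough to be a near-miss and would not justify a comment alone.

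Three other strong inferences also fail:

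- *That a one-sided test is the only reading that fits.* Covariate adjustment and a weakly correlated joint test also reach about .90, and the joint test is close to the multivariate model the SAP names. H.1 to H.3 are directional (for example "more likely to receive the COVID-19 vaccine"), but no one-sided test is stated. The chi-square tests do not settle sidedness, since they are named only for baseline comparisons.
- *That the repeated-measures design cannot help the primary outcomes.* Baseline completion would be constant among people unvaccinated at entry, but none of the eleven eligibility criteria requires that. The SAP plans to compare acceptance and completion between arms at baseline, and it plans other covariates.
- *That attrition will be high.* Protocol Section 8 reports difficulty with follow-up, but as the reason for adding telephone and video interviews. It also provides reminders and tracing through contacts, and Section 11 adds a payment for the follow-up survey. The rate is unknown in either direction.

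It is also fair that clinic randomisation is a larger threat to power than the difference between .90 and .81. Addressing it would still leave the participant-level inputs of this sentence unstated.

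**Conclusion.** The stated .90, with attrition said to be already covered, is not supported by the documents. On the conventional reading, 527 analysed per arm are needed and 500 are recruited. The shortfall against .90 is about 1.5 points with no loss, 5 at 10%, 9 at 20% and 12 at 25%. This rests on a standardised difference of .20, a two-sided unadjusted test, independent participants and assumed attrition rates.

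The conclusion is that the claim is unsupported, not that it is proven wrong. Nor is .81 at 20% attrition a ceiling: covariates explaining about 24% of the variance would bring a participant-level analysis back to .90 at the same number. But every reading that rescues the figure needs an input that appears in neither document, and all of them set aside the six-clinic randomisation, which lowers power further.

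**What to change.** Replace the sentence in the SAP and its copy in Protocol Section 8 with what 500 enrolled per arm delivers, naming the test, sidedness, effect metric, assumed attrition and analysed number. For example, with 20% as a placeholder for the team's own rate:

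*With 500 enrolled per arm and an assumed 20% attrition (400 analysed), an unadjusted two-sided .05 comparison has about .81 power for a standardised difference of .20, or .90 power for .23, if participants are treated as independent; clinic randomisation reduces this further.*

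Write about .81, not at most .81. Remove "accounting for moderate participant attrition" from beside the .90 unless the adjustment, correlation or one-sided test that supports it is stated with its value.

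The cost is one sentence in two places, with no extra participants or procedures. The downside is a less favourable stated power.
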